Appendix C

CINJ 002011 COVID-19 Baseline Questionnaire

Your Medical History

Are you completing this Baseline Questionnaire online or in person at a study site? Online In person at study site

Please indicate if you have been diagnosed with or treated for one or more of the following conditions:

- Diabetes mellitus
- High blood pressure or hypertension
- Asthma
- Chronic bronchitis, emphysema, or chronic obstructive pulmonary disease (COPD)
- Another chronic lung disease (specify): _____
- Coronary artery disease, peripheral artery disease, angina, or heart attack (myocardial infarction)
- Congestive heart failure
- Stroke or transient ischemic attack (TIA)
- Atrial fibrillation
- Cancer other than non-melanoma skin cancer
- Chronic kidney disease (CKD)
- Crohn's disease, ulcerative colitis, or inflammatory bowel disease (IBD)
- Rheumatoid arthritis (RA), psoriasis, systemic lupus, multiple sclerosis, or another disorder for which you take medicine to lower your immune system (immunosuppressant)

Please write the names of all the medicines you have taken in the last week, including over-the-counter medicines, supplements, probiotics:

Medicine 1	_____	Medicine 8	_____
Medicine 2	_____	Medicine 9	_____
Medicine 3	_____	Medicine 10	_____
Medicine 4	_____	Medicine 11	_____
Medicine 5	_____	Medicine 12	_____
Medicine 6	_____	Medicine 13	_____
Medicine 7	_____	Medicine 14	_____

List any other medicines you take here, separated by commas.

Do you ever take a probiotic?

- 0, Never
- 1, Occasionally, such as when I take antibiotics or have diarrhea
- 2, Yes, regularly

Have you ever received pneumococcal vaccines (Pevnar-13 or Pneumovax-23)?

- 0, No
- 1, Yes
- 2, I don't know

Did you receive the influenza vaccine this past season?

- 0, No
- 1, Yes
- 2, I don't know

In the last week, have you had a new fever > 100° F?

- 0, No
- 1, Yes
- 1, I felt feverish but did not take my temperature.

In the last week, have you had a new cough?

- 0, No
- 1, Yes

In the last week, have you felt new shortness of breath or had new difficulty breathing?

- 0, No
- 1, Yes

In the last week, have you had new vomiting?

- 0, No
- 1, Yes

In the last week, have you had new diarrhea (multiple watery stools)?

- 0, No
- 1, Yes

In the last week, have you had a new loss of smell or taste?

- 0, No
- 1, Yes

[figure not shown]
Indicate when you have lost your sense of smell, taste, or both.

- 0, Smell
- 1, Taste
- 2, Both smell and taste

In the last week, have you received care or been tested for coronavirus in an office or clinic?

- 0, No
- 1, Yes, for one or more of the above symptoms
- 2, Yes, for another reason

What diagnosis (or diagnoses) were you given?

Name of emergency contact: _____

Relationship of emergency contact:

- 0, Spouse/Partner
- 1, Child
- 2, Parent
- 3, Sibling
- 4, Grandparent
- 5, Aunt
- 6, Uncle
- 7, Cousin
- 8, Unrelated Adult/Roommate
- 9, Friend
- 10, Neighbor
- 11, Other (specify below)

Mobile phone number of emergency contact: _____

Name of second emergency contact: _____

Relationship of second emergency contact:

- 0, Spouse/Partner
- 1, Child
- 2, Parent
- 3, Sibling
- 4, Grandparent
- 5, Aunt
- 6, Uncle
- 7, Cousin
- 8, Unrelated Adult/Roommate
- 9, Friend
- 10, Neighbor
- 11, Other (specify below)

Mobile phone number of second emergency contact:

- How would you describe your ethnicity?
- 1, Hispanic, Latino, Latina, or Latinx
 - 2, Middle Eastern or North African descent
 - 0, None of the above
 - 3, Prefer not to report

- How would you describe your race?
- 1, American Indian or Alaskan Native
 - 2, Asian
 - 3, Black or African American
 - 4, First Nations, Inuit, or Métis
 - 5, Native Hawaiian or other Pacific Islander
 - 0, White
 - 6, Other
 - 7, Prefer not to report

Appendix D

CINJ 002011 COVID-19 Follow-up Questionnaire

Day: _____

Patient: _____

Update on how you are feeling

In the last day, have you had a new fever > 100° F?

- 0, No
- 1, Yes
- 1, I felt feverish but did not take my temperature.

In the last day, have you had a new cough?

- 0, No
- 1, Yes

In the last day, have you felt new shortness of breath or had new difficulty breathing?

- 0, No
- 1, Yes

In the last day, have you had new vomiting?

- 0, No
- 1, Yes

In the last day, have you had new diarrhea (multiple watery stools)?

- 0, No
- 1, Yes

In the last day, have you had a new loss of smell or taste?

- 0, No
- 1, Yes

Indicate when you have lost your sense of smell, taste, or both.

- 0, Smell
- 1, Taste
- 2, Both smell and taste

In the last day, have you had any additional symptoms?

- 0, No
- 1, Yes

In the last day, have you taken any new medications?

- 0, No
- 1, Yes

If so please list below

In the last day, have you receive care or had tests in an office or clinic? 0, No

1, Yes

Document test or procedures

Please provide all temperatures recorded on your log in the last 24 hours.

AM: _____

Mid-day: _____

Afternoon: _____

Night: _____

In the last day, have you taken your study medication as prescribed? 0, No

1, Yes

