 - Study participant doses self with prescribed study medications (unless inpatient)
 - Assessment completed by Research Nurse. May be conducted by phone.
 - Complete follow-up COVID signs and symptoms questionnaire (Appendix D)
 - Review of daily temperatures
 - Review of medication compliance

- Record standard of care treatments and/or procedures prescribed
- Day3 or 4 and Day 6

Repeat physical examination

- Labs: CBCD, Ferritin, D-Dimer, LDH, CRP and Troponin (8 mL) (Day 6 only)
- Collect research specimens: saliva, oropharynx swab and whole blood (16 mL)
- Day 10 (+/- 1 day)
 - Repeat physical examination
 - Labs: CBCD, Ferritin, D-Dimer, LDH, CRP and Troponin (8 mL)
- o Day 11-20 Daily Follow-up
 - Assessment completed by Research Nurse. May be conducted by phone.
 - Review of symptoms
 - Review of daily temperatures
 - Adverse events
 - Record standard of care treatments and/or procedures prescribed
- Treatment Period For those study participants randomized to Arm 3:
 - o Days 1 5
 - Study participant doses self with prescribed study medications (placebo), unless inpatient.
 - Assessment completed by Research Nurse. May be conducted by phone.
 - Complete follow-up COVID signs and symptoms questionnaire (Appendix D)
 - Review of daily temperatures
 - Review of medication compliance
 - Adverse events
 - Record standard of care treatments and/or procedures prescribed
 - Day3 or 4 and Day 6
 - Repeat physical examination
 - Labs: CBCD, Ferritin, D-Dimer, LDH, CRP and Troponin (8 mL) (Day 6 only)
 - Collect research specimens: saliva, oropharynx swab and whole blood (16 mL)
 - If patient continues to have symptoms of COVID-19 on Day 6, will initiate Hydroxychloroquine sulfate for home administration.
 - o Day 10
 - Repeat physical examination
 - Labs: CBCD, Ferritin, D-Dimer, LDH, CRP and Troponin (8 mL)
 - o Day 11-15
 - Study participant doses self with prescribed study medications (unless inpatient)
 - Assessment completed by Research Nurse. May be conducted by phone.
 - Complete follow-up COVID signs and symptoms questionnaire (Appendix D)
 - Review of daily temperatures

Confirmed COVID-19

Protocol Version Date: 08-May-2020

OI

- Adverse events
- Record standard of care treatments and/or procedures prescribed

Day 15-20 - Daily Follow-up

- Assessment completed by Research Nurse. May be conducted by phone.
- Review of symptoms
- Review of daily temperatures
- Adverse events
- Record standard of care treatments and/or procedures prescribed

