Follow-up Period for All Arms

- Weekly Follow-up for Four (4) Weeks (+/- one day) from last dose of treatment
 - Assessment completed by Research Nurse. May be conducted by phone.
 - Review of symptoms
 - . Review of daily temperatures
 - Adverse events
 - Record standard of care treatments and/or procedures prescribed

Monthly Follow-up for Six (6) Months (+/- one week)

- Assessment completed by Research Nurse. May be conducted by phone.
- Review of symptoms
- Review of daily temperatures
- Adverse events
- Record standard of care treatments and/or procedures prescribed

2. Treatment Plan:

Dosage and Administration

Hydroxychloroquine sulfate 200 mg po TID X 10 days Arm 1:

Azithromycin 500 mg po on day one, followed by 250 mg po QD X 4 days

- Arm 2: Hydroxychloroquine sulfate 200 mg po TID X 10 days
- Arm 3: Placebo Days 1-6, following viral sampling on day 6
 - Hydroxychloroquine sulfate 200 mg po TID x 10 days

Dose Modification:

Hydroxychloroguine

- For grade 1 or 2 intolerability: allow patient to hold one dose and resume as tolerated without adjustment
- For grade 3 or 4 toxicity: hold one dose and resume at BID dosing to complete the original 10 days of dosing
- For second episode grade 3 or 4 toxicity: hold next dose and resume at once daily dosing to complete the original 10 days of dosing.

Hydroxychloroquine sulfate

One hydroxychloroquine sulfate tablet contains 200 mg of hydroxychloroquine sulfate, which is the equivalent to 155 mg base.

For this study, dosing will be 200 mg TID PC x 10 days with or without azithromycin (depending on randomization).

Take hydroxychloroquine sulfate tablets with a meal or a glass of milk when permissible.

Azithromycin

For this study, dosing will be azithromycin 2 x 250 mg (500 mg) on Day 1, followed by 1 x 250 mg daily x 4 (D2 thru 5) with HCQ 200 mg TID PC x 10 days beginning on Day 1 (depending on randomization).

Placebo

Arm 3 only. For this study, participants will be provided 30 placebo tablets to maintain the blind between Arm 2 and Arm 3. Dosing will be placebo tablet x 3 daily (D1 thru 6).

Concomitant Medications & Supportive Guidelines

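### The daily symptom form asks only about new symptoms, so as worded it cannot date the resolution of cough, shortness of breath or loss of smell or taste

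*SAP*

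**What the plan says.** Protocol Sections 1.1 and 1.3 F list time to resolution of symptoms as a secondary endpoint and give the symptom questionnaire as its source. Protocol Section 1.5 and SAP Section 6.1 (Other analyses) repeat that source and allow Kaplan-Meier curves and a log-rank test. Section 1.3 F also labels the secondary endpoints descriptive.

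Protocol Section 1.3 A makes Appendix D the follow-up questionnaire and lists it on treatment days under an assessment done by a research nurse, possibly by phone.

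Appendix D names six symptoms: fever, cough, shortness of breath, vomiting, diarrhea, and loss of smell or taste. Each item asks about a new occurrence in the last day, for example "In the last day, have you had a new cough", "In the last day, have you felt new shortness of breath or had new difficulty breathing" and "In the last day, have you had a new loss of smell or taste". The answers are *No* or *Yes*, with one further option for feeling feverish without a measurement. The form also says "Please provide all temperatures recorded on your log in the last 24 hours". The baseline form, Appendix C, uses the same construction over a longer window: "In the last week, have you had a new cough".

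**The concern.** Dating resolution requires knowing, day by day, whether a symptom is still there. A question about new onset does not supply that. If a continuing symptom and a vanished one produce the same answer, the resolution date is not in the data, and no later analysis can recover it from this form. Mixed interpretation is also a problem: if some patients or nurses take *new* as new since yesterday and others as new with this illness, the endpoint combines two different quantities.

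At stake are the medians, the Kaplan-Meier curves and the optional log-rank comparison for one secondary endpoint.

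**Working it through.** The documents give no sample size, power or assumed resolution time for this endpoint, so there is no figure to reproduce. The check is a reading of the form against the endpoint, followed by simple algebra on labelled assumptions.

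**1. Does any Appendix D item record persistence?**
- Cough, shortness of breath, loss of smell or taste: new in the last day only. No option for still present or resolved.
- The follow-up question on smell and taste offers only the type of loss (smell, taste or both).
- Vomiting and diarrhea: same wording, but a fresh episode can still be answered *Yes*, so the problem is weaker.
- Fever: same wording, but the logged temperatures show its course.
- Additional symptoms: does not ask whether a listed symptom continues.

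**2. Two hypothetical patients, both with cough at baseline.** A's cough stops before Day 1. B's lasts through Day 9, so B's first cough-free day is Day 10. Read literally, both answer *No* on each of Days 1 to 10, and their forms are identical. If *No* is scored as resolved, both resolve on Day 1. That is right for A and 10 − 1 = 9 days too early for B.

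**3. Direction of the effect on an arm comparison.** Assume a share f of patients is read literally, the same in both arms and unrelated to how long symptoms last. Assume also that *No* is scored as resolved, that literal readers are recorded as resolved when logged fever ends (or on Day 1 if there is none), and that there is no censoring. Let D be the true difference between arms in mean resolution time and D_fever the difference in that literal-reader date. Then

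recorded difference = (1 − f) × D + f × D_fever.

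- If D_fever = 0: f = 0.25 leaves 0.75 D, and f = 0.50 leaves 0.50 D.
- If D_fever = D: the recorded difference is D for any f, so nothing is lost.
- If f = 0: no effect.

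Neither f nor D_fever is in the documents. The algebra shows direction and what the size depends on; it does not estimate the size.

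**4. Baseline.** Read literally, Appendix C misses a symptom that began more than a week earlier, and the inclusion criteria set no limit on symptom duration. However, the Day 0 severity score in Protocol Section 1.3 A scores cough and shortness of breath with no requirement that they be new. SAP Section 6.1 stratifies randomization by severity, so the score is needed for every patient. The baseline gap therefore mainly concerns loss of smell or taste lasting more than a week.

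**5. Other symptom records.** Protocol Section 1.3 lists physical examinations on Day 3 or 4, Day 6 and Day 10. It also lists a nurse "Review of symptoms" from Day 11 in Arms 1 and 2, from Day 15 in Arm 3, and then weekly and monthly. Section 1.3 C.5 mentions clinician assessment for symptom improvement, and Section 1.3 D lists disease symptoms as a data point. None is named as the source for time to resolution, and none is said to record the presence of each listed symptom.

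**The case against.** The best defence is that the literal reading is not the intended one. Taken literally, the daily cough item would be *No* on almost every day for almost everyone and would serve little purpose. Appendix C asks about asthma, COPD and other chronic lung disease before it asks about new symptoms, which suggests that *new* means not the patient's chronic symptom. The form sits under a research-nurse assessment, and trained staff may apply one convention. The step in Section 1.3 A for Arm 3 at Day 6 requires someone to judge whether symptoms continue, so persistence is assessed at least then. The data capture plan mentioned in Section 1.3 D is not among the documents and may define the item.

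Much of this stands. It makes the benign reading plausible and is why no share of literal readers can be asserted. It does not settle the matter. The window of the last day points towards new since yesterday, and the same form asks about new medications in the last day, apparently in that sense. No visible text chooses between the meanings or gives a rule that turns answers into a date, even on the benign reading.

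A reader might go further and infer that the trial collects nothing on symptom persistence, that baseline symptoms generally go unrecorded, or that a definite loss of power can be quoted. The documents support none of these. Other records exist, the Day 0 score covers cough and shortness of breath, and any power figure would rest wholly on assumed inputs.

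**Conclusion.** The point holds as a defect of wording with a limited reach. As printed, the only named source for time to resolution can record a persisting cough, shortness of breath or loss of smell or taste exactly as it records a resolved one. Fever is not affected, and vomiting and diarrhea are affected less.

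The size is unknown. It depends on how many patients or nurses take *new* literally, on whether *No* is scored as resolved, and on whether the other records are used. If *No* is scored that way, recorded resolution is too early; if the literal share is similar across arms, differences tend to shrink. The primary Day 6 virological endpoint is untouched, and this endpoint is labelled descriptive. It is still worth correcting, because the descriptive medians would be wrong too, the missing information cannot be restored from the form, and the remedy is cheap. Confidence is moderate, since the data capture plan could resolve the ambiguity.

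**What to change.** 1. **Appendix D:** for each listed symptom, ask whether it was present in the last 24 hours beyond the patient's usual state before COVID-19.
2. **Appendix C:** record whether each listed symptom is present now, whatever its onset.
3. **SAP Section 6.1:** state that resolution is dated from these presence items.
4. **If forms are already in use:** give the research nurses a one-line definition of *new* as present and not usual before COVID-19, and flag forms completed before that for a sensitivity analysis. If the data capture plan already defines the word, print that definition on the form.

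The cost is a minor form amendment with IRB review and one SAP sentence, with no extra visits. Protocol Section 4.3 expects enrollment to take only 30 to 40 days, so a mid-trial change may leave two wordings within one endpoint; hence the flag.

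Two neighbouring matters are separate and optional: whether resolution should require consecutive symptom-free days, and the mismatch in questionnaire days between Protocol Section 1.3 (for Arm 3, none listed on Days 6 to 10) and the daily schedule in Appendix A.
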